3.3 Secondary Endpoints

Secondary endpoints will be assessed as below over 8 weeks after initiation of depatuxizumab mafodotin treatment, assessed separately for the chemoradiation phase and adjuvant phase, as appropriate, as different doses of depatuxizumab mafodotin are used in each phase. The effectiveness of the initial prophylactic strategy and of the BCL-intervention will be assessed separately, as will be resolution of OSEs after interruption/discontinuation of depatuxizumab mafodotin.

Effectiveness of Prophylactic Regimen	Effectiveness of BCL Intervention

 • Maximum change from baseline on LogMAR scale • Time to BCL intervention • Dose interruptions due to OSEs (% subjects) • Dose reductions due to OSEs (% subjects) • Cumulative dose of depatuxizumab mafodotin received (mg/kg) (during chemoradiation and during adjuvant treatment) • CEAE grade, at each visit 	
 • Change in LogMAR (pre- to post-intervention, then followed longitudinally) • Recovery to < 3-line decline from baseline (< +0.3 LogMAR) in visual acuity (% subjects) • Dose interruptions due to OSEs (% subjects) • Dose reductions due to OSEs (% subjects) • Time to restart depatuxizumab mafodotin (if interrupted) • CEAE grade, at each visit, post BCL intervention
Resolution of OSEs	

 • Time to OSE symptom resolution after drug discontinuation (reversibility) • Time to re-initiation of depatuxizumab mafodotin after dose interruption 	

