During the Adjuvant Phase, all subjects will receive oral TMZ (150 – 200 mg/m²) once daily, on Days 1 – 5 of each 28-day cycle, for 6 – 12 cycles, depending on local standard of care. All subjects will receive depatuxizumab mafodotin at 1.25 mg/kg IV infusion once every 2 weeks (on Day 1 and Day 15 of each 28-day cycle) for 12 cycles. Adjuvant treatment will be discontinued upon determination of tumor progression as defined by Response Assessment in Neuro-Oncology Working Group (RANO) criteria (Operations Manual, Appendix I), unacceptable toxicity, or refusal to continue study treatment.

Subjects will be randomized to 1 of 3 prophylactic eye treatment arms (1:1:1), to be administered with each infusion of depatuxizumab mafodotin (during both Chemoradiation Phase and Adjuvant Phase):

- Arm A (SS) – Standard Steroids
- Arm B (SS/VC) – Standard Steroids + Vasoconstrictor + Cold Compress
- Arm C (ES/VC) – Enhanced Steroids + Vasoconstrictor + Cold Compress

Subjects will be monitored at regular intervals for OSEs by AE reports and by ophthalmology examinations (including slit lamp examination and visual acuity testing).

[figure not shown]
For subjects who demonstrate inadequate control of OSEs with the initial prophylactic strategy, according to predefined criteria for loss of visual acuity and/or OSE symptom severity, intervention with a BCL will first be employed (Figure 2). Subjects who continue to demonstrate inadequate response to BCL intervention (CEAE Grade 3 or higher OSE symptom severity) will be eligible for unrestricted OSE management according to investigator discretion. In this case, depatuxizumab mafodotin dose interruption and/or reduction may be used, and any available prophylactic (including addition of ES and VC regimens if not used initially) or supportive care measures may be employed without restriction, at the discretion of the investigator.

Subjects who complete 8 weeks of adjuvant therapy (8 weeks after the first dose of adjuvant depatuxizumab mafodotin) will be allowed to enter the Investigator Discretion phase regardless of CEAE Grade, visual acuity or BCL intervention.

Visual acuity will be measured using the LogMAR scale for visual acuity, while OSE symptom severity will be measured by the Corneal Epithelial AE grading scale (see Section 6.1 and Operations Manual, Section 4.3), which was developed by the sponsor for assessing and managing corneal epitheliopathy associated with ADCs.

[figure not shown]

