- As per TMZ prescribing information, during the 28-day cycle of TMZ, a blood count for ANC and platelets should be performed 21 days (\pm 2 days) after the start of each TMZ cycle. If the ANC falls below 1,500/ μ L or if the platelet count falls below 100,000/ mm^3 , then blood counts should be performed weekly until recovery to these levels before TMZ dosing. A certified local lab may be used instead of central lab; if so, ANC and platelet results should be reported in the eCRF. Day 22 testing may be omitted for cycles in which TMZ is not administered or if local prescribing information allows for a different testing schedule for ANC and platelets.
- Final Study Drug Visit to be performed approximately 14 days after last dose of depatuzumab mafodotin.
- To be performed 35 days (\pm 3 days) after the last dose of depatuzumab mafodotin. If the Final Study Drug Visit is more than 35 days after the last dose of study drug, then 35-day safety follow-up procedures will not be performed.
- Physical exams will be performed only as needed for safety management and AE/SAE reporting.
- Ophthalmology exams will be performed only as needed for safety management and AE/SAE reporting. The last ophthalmology exam following discontinuation of depatuzumab mafodotin may be done at the 35-Day F/U or 49-Day F/U Visit. Targeted ophthalmology exam data will not be collected by the Sponsor.
- TMZ will be administered once daily on Days 1 through 5 of each 28-day cycle for 6 cycles per the local prescribing information.

- i. Depatuxizumab mafodotin infusion will be administered on Day 1 and Day 15 of each 28-day cycle for 12 cycles.
- j. Patient will receive management of ocular side effects as per investigator discretion. In this case, depatuxizumab mafodotin dose interruption and/or reduction may be used, and any available prophylactic or supportive care measures may be employed without restriction, at the discretion of the investigator. Refer to Section 5.7 of the protocol.
- k. If the subject is unable to return to the site for the Day 49 Follow-Up Visit, a phone call may be conducted to obtain AE/SAE and concomitant medication information.

Depatuxizumab Mafodotin Administration and Individual Subject Discontinuation

Depatuxizumab mafodotin will be administered as described in the protocol.

Subjects may continue receiving depatuxizumab mafodotin while drug supply is available, as long as disease progression has not been determined.

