11.2 Analysis of Primary Endpoint

The proportion of patients who met the primary endpoint defined as (a) either $\geq +0.3$ change on LogMAR scale in baseline adjusted visual acuity or (b) incidence of \geq Grade 3 Corneal Epithelial Adverse Event (CEAE, CMQ: 80000184), anytime over 8 weeks after initiation of Depatux-M and prior to BCL intervention will be summarized by treatment arms and in overall population. This analysis will also be repeated for the Post-BCL intervention period. For the Post-BCL intervention period, analysis will be

limited to the patients who received BCL intervention and baseline will be re-set to the last assessment prior to start of BCL intervention.

Time to the first occurrence (onset) of any CEAE will be assessed using Kaplan Meier methodology and median time to first onset of any corneal AE (along with 95% CI). This analysis will be repeated for Grade 3 or higher corneal AEs.

Time to onset will be measured in days relative to the date of first dose date to the start date of the first occurrence of CEAE. If a subject has not experienced an CEAE, the subject will be censored on the subject's last assessment date (i.e., the day of the subject's last known laboratory assessment, last known vital sign assessment, last known physical exam, last known ocular exam, last known tumor assessment, or last known follow-up visit, whichever is the latest) or 49 days from the subject's last treatment (Depatux-M), whichever is earliest. If the subject has no post-baseline assessment, the data will be censored on the day of first dosing date.

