11.3 Analysis of Secondary Endpoints

The maximum change from baseline in visual acuity on baseline corrected LogMAR scale prior to BCL intervention will be summarized by treatment arms and in overall population.

Kaplan-Meier plot for Time to BCL intervention will be produced. Time to BCL is defined as time from the randomization to the start date of BCL (as recorded in "Study Drug Administration - Bandage contact lens" CRF page). For subjects did not use BCL will be right-censored on the last assessment date.

In addition, Time to either $\geq +0.3$ change on LogMAR scale in baseline adjusted visual acuity or grade 3 or higher CEAE prior to BCL intervention will also be analyzed. For this analysis, $+0.3$ change on LogMAR scale in baseline adjusted visual acuity before the start date of BCL or grade 3 or higher CEAE prior to the start date of BCL intervention will be considered as events. If a patient receives BCL intervention without experiencing any one of these two events will also be considered as event on the start date of BCL

intervention. If a patient neither receives BCL intervention nor experiences any one of these two events, his/her time will be right-censored on the last assessment date.

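### Time to BCL and the LogMAR/CEAE/BCL composite run past the end of the assigned eye regimen and of scheduled eye-event collection; the main analysis should follow the protocol's 8-week windows

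*SAP*

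**What the plan says.** **SAP.** Section 11.3 gives time to BCL an origin and an event but no upper limit: "Time to BCL is defined as time from the randomization to the start date of BCL", and "For subjects did not use BCL will be right-censored on the last assessment date". A second analysis in 11.3 takes the time to a LogMAR loss of 0.3 or more or a Grade 3 or higher CEAE before any lens. It also counts a lens fitted without either criterion: "If a patient receives BCL intervention without experiencing any one of these two events will also be considered as event on the start date of" the lens. For a subject with none of these, "his/her time will be right-censored on the last assessment date".

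Section 11.2 adds time to first CEAE and to first Grade 3 or higher CEAE, censored at the last assessment or "49 days from the subject's last treatment (Depatux-M), whichever is earliest". For that purpose laboratory, vital-sign, physical, ocular and tumour assessments and follow-up visits all count as assessments. Section 11.3 uses the same term without redefining it. The 8-week limit appears only for the primary endpoint (5.3.1 and 11.2).

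**Protocol.**
- Section 3.3, which lists time to BCL: "Secondary endpoints will be assessed as below over 8 weeks after initiation of depatuxizumab mafodotin treatment", with the two phases taken separately as appropriate. Section 4.1 assesses the prophylactic strategies in the first 8 weeks of each phase.
- Section 4.1, repeated in 5.7 and 6.3: subjects who complete 8 weeks of adjuvant therapy "will be allowed to enter the Investigator Discretion phase regardless of CEAE Grade, visual acuity or BCL intervention". Section 5.7 then places no restriction on eye measures, and 6.3 lists enhanced steroids and vasoconstrictor with cold compress among the options.
- Appendix E, for subjects who continue after the amendment: "any available prophylactic or supportive care measures may be employed without restriction, at the discretion of the investigator". Its schedule has no CEAE row. Eye exams are done only as needed for safety, and the sponsor does not collect targeted exam data.

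**The concern.** Curves of this kind, shown by arm, are read as evidence on how well each assigned regimen holds off ocular side effects. That reading needs three things: the assigned regimen is in force, a lens start means the regimen failed, and events are being looked for.

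After release to investigator discretion, the first two are no longer assured. An Arm A subject may receive Arm C's components while keeping one arm label, because SAP 6.0 classifies by prophylactic treatment received and gives no rule for a change. A lens no longer has to follow the trigger criteria, yet any lens start is an event in both SAP 11.3 analyses.

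After Appendix E procedures begin, the third fails as well. Scheduled CEAE grading and targeted visual-acuity data stop, but laboratory and adverse-event visits go on. If the SAP 11.2 meaning of last assessment also applies in 11.3, those visits keep extending event-free time.

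**Working it through.** **1. The plan's own figures.** Table 6 (Protocol 7.1) is the only design calculation. It reproduces as p ± 1.96 × √(p(1 − p)/30). For 8/30 this is 0.267 ± 1.96 × 0.0807, or 10.8% to 42.5%; for 14/30 it is 0.467 ± 1.96 × 0.0911, or 28.8% to 64.5%. The other two rows also agree. The point does not rest on this table; its rates serve below only as assumed 8-week event rates.

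**2. When the regimen is released.** Inputs from Protocol 4.1: chemoradiation 42 to 49 days; gap about 28 days (42 is a notification threshold, not a maximum); release 8 weeks (56 days) after the first adjuvant dose. Days are counted from first dose.
- Short case: 42 + 28 + 56 = day 126, week 18.
- Long case: 49 + 42 + 56 = day 147, week 21.
- End of cycle 12: 42 + 28 + 336 = day 406, or 49 + 42 + 336 = day 427.

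The protocol's adjuvant window (8 weeks from first adjuvant dose) closes at the release point, so the protocol's windows stay within the period when the assigned regimen was required. SAP 11.3 does not stop there. Appendix E management has no 8-week wait and, on its own schedule, could apply from adjuvant cycle 1 (42 + 28 = day 70, week 10). Time to BCL is counted from randomization, so on that clock each point falls later by the randomization-to-dose interval, which is not given.

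**3. Which analyses are exposed.**

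| Analysis | Limit in SAP | Runs past release? | Own 8-week limit in Protocol 3.3? |
|---|---|---|---|
| Primary proportion | 8 weeks, before BCL | No | Not applicable (8 weeks set in 3.2) |
| Time to BCL | Last assessment | Yes | Yes |
| Composite | Last assessment | Yes | Not listed |
| Time to CEAE | Last assessment or last dose + 49 days | Yes, but capped | Not listed |

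Subjects who reach investigator discretion through an inadequate response to BCL already have their event. Only event-free subjects carry the problem in the two 11.3 analyses.

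**4. How much follow-up could be involved (assumed inputs).** Take a constant event hazard λ = −ln(1 − p₈)/8 per week with p₈ from Table 6, and a constant exit hazard μ = ln 2/34.8, using the sister trial's median PFS of 8.0 months (34.8 weeks; Protocol 2.2). The share of at-risk time to week 58 that falls after week 18 is (e^(−18h) − e^(−58h))/(1 − e^(−58h)), with h = λ + μ.
- p₈ = 26.7%: h = 0.0388 + 0.0199 = 0.0587; (0.348 − 0.033)/0.967 = 0.325.
- p₈ = 46.7%: h = 0.0786 + 0.0199 = 0.0985; (0.170 − 0.003)/0.997 = 0.167.

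So the share is roughly 17% to 33%. The early stop lowers it further: the protocol and SAP say most subjects lacked long-term follow-up.

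**5. What switching could do (assumed inputs).** This is a simulation with exponential times, 3,000 per arm, no drop-out, the Table 6 rates in Arm A, a true C-versus-A hazard ratio of 0.5, and Arm A switchers taking on Arm C's hazard at week 18. The plan specifies no hazard ratio; it serves here only as a yardstick.

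| Event-free Arm A subjects who switch | Hazard ratio, follow-up to week 58 |
|---|---|
| None | 0.48–0.51 |
| Half | 0.55–0.60 |
| All | 0.61–0.70 |

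Cut at week 18, the ratio is 0.48 to 0.52 throughout. The result depends on the switching share, which the documents do not give.

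**The case against.** The other side has a good deal right.

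- **Nothing inferential depends on it.** Forty subjects were enrolled in three arms, SAP 11.3 plans no arm comparison, and Kaplan-Meier estimates before release are unaffected. A reader can stop at week 18.
- **Following the assigned strategy through later care can be a legitimate treatment-policy summary.** The SAP does not declare one, however, and the protocol's windows point the other way.
- **Time to CEAE is a weak example.** Its 49-day cap matches the SAP's treatment-emergent definition. In the sister trial 94.7% of treated subjects had a corneal epitheliopathy event, and the higher dose comes first, so few subjects may be CEAE-free by week 18.

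Three stronger readings are tempting, and the documents do not support them.

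- A reader might infer that the protocol set an 8-week limit for every one of these endpoints and the SAP removed it. Only time to BCL had such a limit in Protocol 3.3; the composite and time to CEAE are SAP additions, covered only by the general statement in Protocol 4.1.
- A reader might take the calendar as the size of the bias: 280/406 days (69%) and 20 of 27 planned infusions (74%) fall after week 18. These are planned shares, not time at risk, because subjects leave the curves at their event and at progression.
- A reader might infer that the arms must converge toward Arm C. Release is permitted, not required. Those still at risk in the composite have had no lens and neither trigger, so they have little evident reason to escalate, and the text does not appear to prevent Arm C subjects from using less. Discretionary lenses add events, while lost ascertainment removes them.

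What remains is that the main curves have no limit matching the protocol's window, and that under Appendix E they can outlast event collection.

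**Conclusion.** The point holds for time to BCL and the composite in SAP 11.3. As written, lens starts at investigator discretion count as events for the arm, and event-free time can accrue after scheduled CEAE and targeted eye-exam data end. The effect is confined to the tails of descriptive curves, beyond about week 18 from first dose (week 18 to 21 on the calendars shown) or from the start of Appendix E management. A median is affected only if it falls there. The primary endpoint and all planned testing are untouched.

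Neither size nor direction can be stated, because the number of subjects who changed regimen is not given. Two inferences carry the conclusion: that each subject keeps a single arm label, since SAP 6.0 has no switching rule, and that the last assessment in 11.3 means what 11.2 says it means. This is a cheap correction worth making, not a threat to the main result.

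**What to change.** In SAP 11.3:

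1. Make the main analysis of time to BCL and of the composite follow the protocol's window: censor at 8 weeks after the first Depatux-M dose. Where adjuvant data are used, add a separate analysis over the 8 weeks from the first adjuvant dose.
2. Censor earlier, where it applies, at the last scheduled CEAE or ophthalmology assessment before Appendix E procedures began for that subject. The date of the updated consent is a poorer choice, because the documents do not show that eye management changed on that date.
3. List later BCL starts separately. Keep full follow-up as a supplementary curve, labelled as such, with a stated arm rule for subjects who changed regimen.

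In SAP 11.2, time to first CEAE may stay as a treatment-emergent safety summary. It should also be censored at the last CEAE or ocular assessment before Appendix E procedures began, not at a later laboratory or vital-sign date.

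A single cut at 8 weeks after the first adjuvant dose would be simpler. It gives one window of about 18 weeks that includes the recovery gap, so it does not restore the protocol's by-phase 8 weeks.

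The cost is a few SAP sentences, the derived censoring dates, shorter follow-up and a few late events moved to a listing. The adjuvant window also describes only subjects still event-free at the first adjuvant dose, a selected group, and should be labelled that way.

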An interim efficacy analysis based on a data cut of 30 April 2019 was performed by the RTOG Independent Data Monitoring Committee (IDMC), at which time 346 OS events had been observed out of 639 subjects included in the main part of the study. The primary analysis of OS is based on the Intent-to-Treat (ITT) population showed no difference in OS between groups, with a median OS of 18.9 vs. 18.7 months for depatuxizumab mafodotin and placebo, respectively. The weighted ($p = 0$, $\gamma = 0.2$) stratified log-rank test p-value (1-sided) was 0.628, and the observed hazard ratio (HR) (95% CI) for OS was 1.01 (0.82, 1.25). The median PFS was 8.0 vs. 6.3 months for depatuxizumab mafodotin and placebo, respectively, with a stratified log-rank test p-value (1-sided) of 0.029. The observed hazard ratio (HR) (95% CI) for PFS was 0.84 (0.70, 1.02). Preliminary analysis of demographic and clinical characteristics did not reveal any factors predictive of OS benefit for the addition of depatuxizumab mafodotin (ABT-414) to standard RT/TMZ therapy.

Overall, 99.4% and 97.8% of subjects experienced at least 1 adverse event, and 87.3% and 62.3% experienced a Grade 3 or higher AE in the depatuxizumab mafodotin and placebo arms, respectively. Overall, 94.7% and 36.1% of subjects experienced at least 1 ocular adverse event related to corneal epitheliopathy, 61.0% and 0.6% experienced a Grade 3 or higher AE related to corneal epitheliopathy, and 11.8% and 0% discontinued study drug (depatuxizumab mafodotin or placebo) in the depatuxizumab mafodotin and placebo arms, respectively. The most common (> 10%) events related to corneal epitheliopathy included keratopathy, vision blurred, photophobia, dry eye, eye pain, keratitis, and punctate keratitis. Excluding events related to corneal epitheliopathy, events for which the incidence in the depatuxizumab mafodotin group was $\geq 5\%$ greater than in the placebo group included thrombocytopenia, gamma-glutamyltransferase increased, aspartate aminotransferase increased, alanine aminotransferase increased, constipation, blood alkaline phosphatase increased, fatigue, and platelet count decreased. Excluding events related to corneal epitheliopathy, Grade 3 or higher events for which the incidence in the depatuxizumab mafodotin group was at least 5% and was $\geq 2\%$ greater than in the placebo group included thrombocytopenia, gamma-glutamyltransferase increased, and alanine aminotransferase increased.

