5.5 Withdrawal of Subjects and Discontinuation of Study

Each subject has the right to withdraw from the study at any time. In addition, the Investigator may discontinue a subject from the study at any time if the Investigator considers it necessary for any reason, including the occurrence of an adverse event or noncompliance with the protocol.

Each subject must be withdrawn from the study immediately if any of the following occur:

- The subject or subject's legally acceptable representative withdraws consent.
- The subject experiences confirmed disease progression (PD), as determined by 2017 update of the Response Assessment in Neuro-Oncology criteria by Ellingson et al,⁸ as described in Appendix I of the Operations Manual.
- Clinically significant abnormal laboratory results or AEs that rule out continuation of the study drug, as determined by the Investigator or the AbbVie Therapeutic Area Medical Director (TA MD).
- The subject requests withdrawal from the study.
- Eligibility criteria violation was noted after the subject started study drug, and continuation of the study drug would place the subject at risk.
- Introduction of prohibited medications or dosages and continuation of the study drug would place the subject at risk.
- The subject becomes pregnant while on study drug.

- Subject is significantly non-compliant with study procedures, which would put the subject at risk for continued participation in the trial.
- Subject experiences intercurrent illness that prevents further administration of treatment
- Subject experiences excessive toxicity precluding further therapy with depatuxizumab mafodotin, according to the Investigator.
- General or specific changes in the subject's condition render the subject unacceptable for further treatment in the judgment of the Investigator.

A subject may also be withdrawn if:

- The Investigator believes it is in the best interest of the subject.

Subjects unable to continue TMZ due to excessive toxicity will be allowed to continue therapy with depatuxizumab mafodotin until one of the other criteria above is met.

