7.4 Statistical Analyses for Safety

For the primary endpoint of the study, the percentage of subjects with either a ≥ 3 -line decline from baseline ($\geq + 0.3$ on LogMAR scale) in visual acuity (with baseline correction) or \geq Grade 3 OSE severity on the Corneal Epithelial Adverse Event [CEAE] scale will be calculated for each arm and associated 95% confidence intervals will be provided. Comparisons between arms will be made using Chi-square test.

For secondary safety endpoints, continuous variables will be summarized with N, mean, standard deviation (SD), median, minimum, and maximum. Frequencies and percentages will be computed for the category variables. For time to event variables, Kaplan-Meier survival curves with median time and associated 95% confidence interval will be provided.

Detailed statistical analysis methods for primary and secondary safety endpoints will be provided in the statistical analysis plan (SAP).

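### The SAP 11.2 Kaplan-Meier curve for Grade 3 or higher CEAE onset censors death and permanent drug stop, so it overstates the share of subjects ever affected; the 11.3 curves censor deaths too, with a bias that their text leaves undetermined

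*SAP*

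**What the plan says.** - **Method.** Protocol 7.4 names one method: "For time to event variables, Kaplan-Meier survival curves with median time and associated 95% confidence interval will be provided". Neither document plans a cumulative incidence estimate or names a competing event.
- **CEAE onset (SAP 11.2).** The analysis covers any CEAE and is repeated for Grade 3 or higher. "If a subject has not experienced an CEAE, the subject will be censored on the subject's last assessment date" "or 49 days from the subject's last treatment (Depatux-M), whichever is earliest". The last assessment is the latest of laboratory, vital sign, physical, ocular, tumor and follow-up visit dates.
- **Time to BCL (SAP 11.3).** A Kaplan-Meier plot is planned. "For subjects did not use BCL will be right-censored on the last assessment date".
- **Composite (SAP 11.3).** The event is LogMAR decline, Grade 3 or higher CEAE, or BCL start. For a subject with none of these, "his/her time will be right-censored on the last assessment date". Section 11.3 neither defines that date nor mentions drug stop.
- **Primary endpoint (SAP 11.2).** This is a crude proportion, with events counted "anytime over 8 weeks after initiation of Depatux-M and prior to BCL intervention will be summarized by treatment arms".
- **Competing events.** Protocol 5.5 requires withdrawal at confirmed progression. Protocol 2.2 gives the INTELLANCE-1 results: "The median PFS was 8.0 vs. 6.3 months for depatuxizumab mafodotin and placebo, respectively", with median OS of 18.9 months on Depatux-M.
- **Follow-up.** SAP 4.0 reports 40 subjects enrolled, most without long-term follow-up. Under Protocol Appendix E the sponsor no longer collects targeted eye-exam data, while laboratory and adverse event visits go on.

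**The concern.** Kaplan-Meier treats a censored subject as having the same future risk as those who remain. That is reasonable for a data cut. It is not reasonable for a subject who has died, and it is doubtful for one who has stopped Depatux-M, since Protocol 2.1 expects the corneal effects to be transient once treatment ends. Censoring such subjects passes their unrealised risk to those still on drug. The curve then describes a population in which nobody dies or stops.

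The objective is expressed as a percentage of subjects, and readers will tend to read percentages off the curves. SAP 11.4 also reports crude counts of treatment-emergent Grade 3 or higher CEAE with the same 49-day limit. The report could therefore show two different figures for what looks like the same risk, by arm, with about 40/3 = 13 subjects in each.

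**Working it through.** **The plan's own figures.** The only design calculation is Protocol Table 6. It reproduces with the Wald interval p ± 1.96 × sqrt(p(1 − p)/30). For 8 of 30, 0.267 ± 0.158 gives 10.8% to 42.5%, and the other three rows also match. The documents give no figure for the curves.

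**Inputs**
- 8-week event risk p8: 26.7% and 46.7%, the ends of Table 6. Table 6 concerns the composite endpoint, so using it for Grade 3 or higher CEAE is an assumption.
- On-drug event hazard h: −ln(1 − p8)/8 = 0.0388 or 0.0787 per week up to week 8. Afterwards it is 25% or 100% of that (assumed range).
- Stopping hazard c: ln 2/(8.0 × 30.4375/7) = 0.0199 per week, with PFS standing in for drug stop. By week 26, 1 − exp(−0.0199 × 26) = 40% would have stopped.
- Censoring lag L: 5 weeks after progression. Dosing is every 2 weeks, so 49 days after the last dose is taken as 49 − 14 = 35 days after progression.
- No events after stop, independent event and stopping times, and no data cut.

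**Formulas.** With H the cumulative event hazard:
- On drug and event-free: S(t) = exp(−H(t) − ct).
- True cumulative incidence: CI(t) = ∫ h S du over 0 to t.
- Kaplan-Meier risk set: R(t) = S(t) + ∫ c S du over t − L to t.
- Kaplan-Meier limit: 1 − KM(t) = 1 − exp(−∫ λ du), with λ = hS/R.
- Greenwood SE: KM × sqrt(∫ (λ/R) du / n), with n = 40.

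**SAP 11.2 curve, Grade 3 or higher CEAE, week 26**

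| 8-week risk | Late hazard | 1 − KM | CI | Excess (points) | SE | Excess/SE |
|---|---|---|---|---|---|---|
| 26.7% | 25% | 36.0% | 33.2% | 2.8 | 8.1 | 0.34 |
| 26.7% | 100% | 59.9% | 51.7% | 8.2 | 8.8 | 0.93 |
| 46.7% | 25% | 59.3% | 55.0% | 4.3 | 8.4 | 0.51 |
| 46.7% | 100% | 84.0% | 73.6% | 10.4 | 6.9 | 1.50 |

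- Week 8: the excess is 0.3 to 0.5 points.
- Week 52: the excess is 9 to 21 points, but few subjects remain. With an assumed data cut spread evenly over 60 to 450 days, fewer than 3 of 40 are at risk.
- Per arm, dividing by sqrt(3) gives 0.2 to 0.9 SE at week 26.
- Sensitivity to the lag: with L = 7 weeks the week-26 excess is 2.1 to 9.0 points. With censoring at stop itself it is 5.2 to 13.4 points, and 1.9 to 3.2 at week 8.

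**SAP 11.3 curves.** Stopping drug does not end follow-up here, so the figures above do not carry over. Two separate reference cases:
- Only deaths compete and the event hazard continues until death (median OS 18.9 months, c = 0.0084 per week). The excess is 0.8 to 1.4 points at week 8, 2.4 to 6.1 at week 26 and 6.2 to 11.6 at week 52.
- Subjects who stop are assessed for 26 more weeks and have no events. The excess is 0 at week 26 and 2.4 to 6.3 points at week 52.

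Appendix E acts the other way on the composite. If the last assessment includes laboratory or adverse event visits, subjects count as at risk while their acuity goes unrecorded, which lowers the curve.

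**The case against.** **Censoring in 11.3.** A reader might infer that all these curves censor at drug stop and all overstate. The text does not support that. The 49-day cap is in 11.2 only. SAP 5.2 and Protocol 5.6 continue eye follow-up after stop until symptoms resolve, and subjects kept in the risk set remove that part of the bias. For the composite, Appendix E leaves the net direction open. This objection stands.

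**Link to the primary result.** A reader might also infer that the primary result is biased. It is not: it is a crude 8-week proportion. Protocol 3.3 also sets an 8-week window for secondary endpoints, where the 11.2 excess is under 1 point. That stands too, but SAP 11.3 does not truncate its curves and 11.2 sets no 8-week limit on CEAE onset, so the later parts will be shown.

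**Size at 12 months.** Enrollment stopped early and data collection was cut back, so end of data may be the commonest reason for censoring. The 12-month figures lie where almost nobody is observed and should carry no weight.

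**Target of estimation.** Prophylaxis is given only while Depatux-M continues, so risk while alive and on drug is a sensible target, and Kaplan-Meier can estimate it if censoring is independent. But the SAP states no such target and places the curves beside crude percentages. The planned outputs are plots and medians without tests, which limits the harm.

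**Risk in the remedy.** Pooling all discontinuation as one competing event would let an arm with more stopping for eye toxicity appear to have less toxicity. This is a fair point, and the fix allows for it.

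**Conclusion.** The point holds most firmly for the Grade 3 or higher CEAE onset curve in SAP 11.2. Read as the share of subjects ever affected, it is too high by under 1 point at 8 weeks and roughly 3 to 10 points at 6 months, about 0.3 to 1.5 SE with 40 subjects pooled. The size rests on INTELLANCE-1 PFS as a proxy for stopping, Table 6 rates, an assumed late hazard, no events after stop, and complete recording of Grade 3 or higher events up to censoring. The last needs care: the Appendix E schedule has no separate CEAE assessment, although adverse events are still collected.

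For 11.3, deaths are censored without a rule of their own. The documents do not fix the size of the bias, nor its direction for the composite. This is a matter of interpretation and labelling in a descriptive analysis. It does not threaten the primary result, but it is worth correcting because the remedy is cheap.

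**What to change.** 1. **SAP 11.2, Grade 3 or higher CEAE onset.** Add Aalen-Johansen cumulative incidence by arm and overall, with 95% CIs. Competing events are death and permanent Depatux-M stop, the latter dated at last dose + 49 days if the subject is still event-free. Show stops for eye toxicity separately from other stops.
2. **SAP 11.3, time to BCL and the composite.** Add the same estimate with death as the competing event. Keep counting lens or acuity events seen after drug stop. Define the censoring date as the last eye, CEAE or BCL assessment, not any laboratory or adverse event visit.
3. **If Kaplan-Meier is kept.** Label it as risk while alive and under observation, print numbers at risk, and read no percentages from it.

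The cost is a few sentences in the SAP, a standard software option and a little more analysis work. It uses dosing, discontinuation and death data that the study already records. Reported probabilities will be somewhat lower, and some medians may not be reached.
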